3.2.3 Rationale for Endpoints

Nirsevimab is being developed to provide RSV immunoprophylaxis for all infants and young children, including immunocompromised children ≤ 24 months of age. The primary endpoint for this study is safety and tolerability. The standard measures of TEAEs/TESAEs, AESIs, and NOCDs will be used for this assessment. All subjects will be followed for approximately 1 year after dosing with nirsevimab.

Serum concentrations of nirsevimab at selected time points will be evaluated as a secondary endpoint to confirm that serum concentrations are maintained at an efficacious level for at least 5 months after dosing. PK data will be summarized by descriptive statistics. PK data obtained in this study will be compared to the PK data from the Phase 2b, Phase 3, and the Phase 2/3 studies. For infants and children who require hospitalization for LRTI or any respiratory infection, an additional serum sample for measurement of nirsevimab concentration and ADA will be obtained contemporaneous with time of hospitalization.

To determine nirsevimab serum levels post dosing and to correlate with the potential development of ADA, serum concentrations will be measured up to 360 days post dose. ADA to nirsevimab will be measured at selected time points throughout the study and up to 360 days post dose.

This study will also summarize efficacy of nirsevimab in terms of incidence of RSV LRTI. RSV results in a significant burden of disease consisting of hospitalization, visits to the ER, and visits to outpatient clinics. This endpoint is designed to allow the capture of this total burden of disease. A separate endpoint of RSV hospitalization will also be evaluated.

Exploratory endpoints will examine CCI [REDACTED]

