^d Nasal samples will be collected for all LRTIs (inpatient or outpatient) and all subjects hospitalized with any respiratory infection (upper or lower) within 2 days after the diagnosis by a healthcare provider. Blood samples will be collected from all subjects hospitalized with LRTI or any respiratory infection within 2 days following hospital admission.

^e Skin reaction assessment will be done for any post-dosing skin or skin-related reaction regardless of severity, duration, time of onset post dosing, or relationship to investigational product.

^f Telephone contact must be verbal communication. Written communication via text, email, or other written form is not acceptable.

^g HRU includes admission and duration of hospital and ICU stay, number of subjects who require respiratory support and supplemental oxygen use, duration of respiratory support and supplemental oxygen use, number and type of outpatient visits (eg, ER, urgent care, outpatient clinic), and number and days of prescription and OTC medication.

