4.3.3.2 Antidrug Antibody Evaluation

Blood samples to evaluate ADA responses to nirsevimab in serum will be collected according to scheduled time points. Blood samples will also be collected for ADA response from subjects hospitalized with LRTI or any respiratory infection within approximately 2 days following hospitalization. See the collection schedule in Section 4.2. Evaluations will be performed using validated immunoassays.

CCI

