### 4.1 General principles

There are 2 planned analyses for this study: an interim analysis and a final analysis. The interim analysis will be conducted when subjects enrolled globally by the end of 2021 have been followed through Day 151. The final analysis will be conducted when all subjects have completed the last visit of the study (Day 361). The data will be validated as defined in the Data Management Plan.

- For the visit-based summaries for PK/ADA, CCI and clinical laboratory data, the summaries will be based on the scheduled visits using adjusted analysis-defined visit windows. The adjusted analysis-defined windows will be based on the collection schedule listed in the CSP and summaries will be windowed to the closest scheduled visit for those data. Visit windows have been constructed so that every observation collected can be allocated to a particular visit. All data will be included in the listings. If multiple readings are recorded within a single analysis-defined visit window, the following rules will apply: If there are 2 or more valid, non-missing observations within the same visit window, and
  - if they are on different days, then the non-missing one which is closest to the scheduled visit day will be used in the analysis.
  - if they are on the same day which is closest to the scheduled visit day, then the non-missing one with the later collection time will be used in the analysis.
- If 2 or more valid observations are equidistant from the scheduled visit, and
  - if they are on different days, then the non-missing post-dose observation with the earlier collection date will be used in the analysis for the post-baseline observations, and the non-missing pre-dose observation with the later collection date will be used in the analysis for the screening observations.
  - if they are on the same day, then the non-missing observation with the later collection time will be used in the analysis.
- For LRTI visits or unscheduled visits, if 2 or more valid observations are collected on the same day, then the non-missing observation with the later collection time will be included in the analysis.
- If a visit window does not contain any observations, then the data will remain missing.
- For the visit-based summaries for ADA, if both ADA positive and negative samples are available within a subject's visit, ADA positive will be reported.

- For summary Statistics of PK data following rules apply:

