#### 4.2.5.2 Anti-drug antibody (ADA)

Serum samples for ADA assessments will be conducted utilizing a tiered approach (screen, confirm, titer), and ADA data will be collected at scheduled visits shown in the CSP. ADA result from each sample will be reported as either positive or negative; samples without an ADA result will not be imputed. If the sample is positive, the ADA titer will be reported as well. In addition, the presence of neutralizing anti-drug antibody (nAb) and anti-YTE will be tested for all ADA-positive samples using validated ligand-binding assays. The nAb and anti-YTE results will be reported as positive or negative.

The number of subjects in the as-treated population and the as-treated Japan subpopulation (defined in Section 2.1) who fulfil the following the criteria will be determined. The percentage of ADA-positive subjects in each of the categories specified below will be calculated, using the number of subjects with any ADA result at baseline and/or post-baseline during the study as the denominator. A subject is defined as being ADA positive if a positive ADA result is available at any time, including baseline and all post-baseline measurements; otherwise ADA negative. Missing ADA result will not be imputed.

- ADA positive at any visit; the percentage of ADA-positive subjects is known as ADA prevalence.
- Treatment-emergent ADA defined as the sum of both treatment-induced and treatment-boosted ADA; the percentage of subjects fulfilling this criterion is known as ADA incidence.
- ADA positive at both post-baseline and baseline.
- ADA positive post-baseline and not detected at baseline (treatment-induced ADA).
- ADA not detected post-baseline and positive at baseline.
- Treatment-emergent ADA-negative, defined as ADA-positive at any visit but not fulfilling the definition of treatment-emergent ADA-positive.
- Treatment-emergent ADA positive with maximum titer higher than median of maximum titers. The median of maximum titers is calculated based on the maximum titer for each ADA-positive subject within the actual dose administered group; ‘nirsevimab 50mg/100mg’ and ‘nirsevimab 200mg’ (including both baseline and post-baseline measurements).
- Treatment-boosted ADA, defined as a baseline positive ADA titer that was boosted to a 4-fold or higher level (greater than the analytical variance of the assay) following drug administration.

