- Persistently positive ADA, defined as negative at baseline and having at least 2 post-baseline ADA positive measurements with at least 16 weeks (112 days) between the first and last positive measurement or an ADA positive result at the last available assessment.
- Transiently positive ADA, defined as negative at baseline and having at least one post-baseline ADA positive measurement and not fulfilling the conditions for persistently positive.
- nAb positive at any visit (nAb prevalence).

- nAb positive post-baseline only (nAb incidence)
- anti-YTE positive at any visit (anti-YTE prevalence).
  - anti-YTE positive post-baseline only (anti-YTE incidence)

To evaluate the impact of ADA on safety, TEAE and TESAE by MedDRA SOC and PT will be summarized by ADA post-baseline status (ie, at least one post-baseline ADA positive or not through 360 days post dose).

Samples with ADA titer < 50 will be regarded as negative results and samples with ADA titer  $\leq 50$  (borderline positive) will be regarded as positive results. The evaluation on the impact of ADA on PK is described in Section 4.2.5.1.

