**Table 1 Population for medically attend RSV respiratory illness**

Type of Endpoint	Endpoint	Protocol definition of LRTI	RSV test result	Investigators assessment of LRTI/URTI	Setting of care
Secondary Efficacy	MA RSV LRTI	Protocol defined	Positive (central RT-PCR)	LRTI	Inpatient or outpatient
Secondary Efficacy	MA RSV LRTI with hospitalization	Protocol defined	Positive (central RT-PCR)	LRTI	Inpatient

CCI

[figure not shown]
All above stated summaries will be based on observed events and data summary will be presented through 150 days post dose, after 150 days post dose, and through 360 days post dose.

Adverse events associated with all medically attended RSV LRTI will be summarized, as well as categorized by the MedDRA SOC and PT. Summaries will be presented through 150 days post dose, after 150 days post dose, and through 360 days post dose.

[figure not shown]
To evaluate the impact of ADA on efficacy, MA LRTI and MA LRTI with hospitalization will be summarized by ADA post-baseline status (ie, at least one post-baseline ADA positive or not through 360 days post dose).

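### Admission-triggered ADA samples count toward the ADA status used in the ADA-impact tables, which biases detection toward an ADA-hospitalization association (minor)

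*SAP*

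**What the plan says.** **Who is sampled.** Protocol Table 5 and Table 7 schedule post-baseline ADA blood at Days 31, 151 and 361 for every child. Protocol 4.3.3.2 adds a sample triggered by an event: "Blood samples will also be collected for ADA response from subjects hospitalized with LRTI or any respiratory infection within approximately 2 days following hospitalization". The rationale in Protocol 3.2.3 is that "an additional serum sample for measurement of nirsevimab concentration and ADA will be obtained contemporaneous with time of hospitalization". The footnote to Table 5 confirms that the trigger is admission; an outpatient LRTI leads to a nasal sample but no blood sample.

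**How ADA status is used.** On safety, SAP 4.2.5.2 states that "TEAE and TESAE by MedDRA SOC and PT will be summarized by ADA post-baseline status". On efficacy, SAP 4.2.5.3 states that "MA LRTI and MA LRTI with hospitalization will be summarized by ADA post-baseline status". In both places the status is one or more positives after baseline, against none, through 360 days. The general definition in SAP 4.2.5.2 is equally open: a child is positive "if a positive ADA result is available at any time, including baseline and all post-baseline measurements".

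**What the SAP excludes.** SAP 4.1.1 leaves unscheduled-visit data out of by-visit and by-timepoint summaries only. No sentence limits the subject-level status in the impact tables to scheduled samples.

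**The concern.** The grouping variable depends in part on the outcome. A child admitted with a respiratory infection has at least four post-baseline ADA samples instead of three. The extra sample can add a positive but cannot remove one. The same admission counts in the outcome: it is a hospitalized MA LRTI if it meets that definition, and it is a serious event because inpatient hospitalization is a seriousness criterion (Protocol 5.2).

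The ADA-impact tables on efficacy and safety are therefore biased toward showing more hospitalization among ADA-positive children, even if ADA does nothing. Few ADA positives are expected (about 6 per 100 children at the Phase 2b rate), so one child classed positive only on an admission sample can visibly change a table.

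This is separate from the order of ADA and event. It would be present even if ADA had no time trend.

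**Working it through.** The plan gives no figure for this. N of about 100 is descriptive, with no power calculation to reproduce.

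**Inputs from the documents**
- Scheduled post-baseline ADA samples: 3 by the final analysis; 2 for a child followed only to Day 151.
- Phase 2b ADA rate: 52/929 = 5.6% (Protocol 1.4.3).
- Phase 1b/2a ADA rate: 20/71 = 28.2%. Of these 20 children, 18 were positive at Day 361 only (18/68 = 26.5%) and 2 at Day 50 only; none was positive at Day 151 (Protocol 1.4.2).

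**Assumptions**
- No true ADA effect.
- The earlier rates apply to this three-sample schedule.
- 10-30% of children are hospitalized with a respiratory infection, once each unless stated. The documents give no figure.

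**1. Upper bound for one admission: independent, transient positives**

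Per-sample probability q = 1 - (1 - p)^(1/3); probability of ever being positive with k samples = 1 - (1 - q)^k.

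| | p = 5.6% | p = 28.2% |
|---|---|---|
| q | 1.90% | 10.45% |
| Ever positive, 3 samples | 5.6% | 28.2% |
| Ever positive, 4 samples (one admission) | 7.4% | 35.7% |
| Odds ratio, 4 against 3 (final) | 1.35 | 1.41 |
| Odds ratio, 3 against 2 (Day 151 interims) | 1.52 | 1.59 |
| Odds ratio, 5 against 3 (two admissions, final) | 1.70 | 1.88 |

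With 20% hospitalized and one admission each, the final table would show 24.8% hospitalized among ADA positives against 19.7% among negatives at the 5.6% rate, and 24.0% against 18.3% at the 28.2% rate.

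Extra positives per 100 children = 100 x hospitalized share x (ever positive with 4 samples - ever positive with 3):
- 5.6% rate: 0.18, 0.36 and 0.54 at 10%, 20% and 30% hospitalized.
- 28.2% rate: 0.75, 1.50 and 2.25.

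**2. Phase 1b/2a pattern**

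The extra sample matters only for ADA that the scheduled samples miss. Two transient positives in 71 children suggest a chance per extra sample of 2/142 = 1.4% to 2/71 = 2.8%. Ever positive = 28.2% + (1 - 28.2%) x 1.4% = 29.2%, or with 2.8%, 30.2%. The odds ratios are 1.05 and 1.10.

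This study has no scheduled ADA sample between Day 31 and Day 151. A transient positive near Day 50 would go unseen in a child who was not admitted, but could be seen in one admitted at that time.

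**3. Lower bound**

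If ADA persists to a later scheduled sample and that sample is taken, the extra sample changes no child's status. The odds ratio is 1.0.

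**4. Offset**

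If positives arise mainly at Day 361, hospitalized children who die or miss that visit lose their likeliest positive sample. In the Phase 1b/2a pattern, the excess of missing Day 361 samples that cancels the bias is (29.2% - 28.2%)/26.5% = about 4 percentage points, up to (30.2% - 28.2%)/26.5% = about 8.

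**5. Check of the fix**

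In a simulation of 2 million children under model 1 with 20% hospitalized, taking status from scheduled samples only gives 20.1% against 20.0% hospitalized (ADA positive against negative) at the 5.6% rate, and 20.0% against 20.0% at the 28.2% rate.

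**The case against.** **It may not bite.** The odds ratios of 1.35 and above need independent transient positives. The documents' own infant data look different: 18 of 20 Phase 1b/2a positives were seen at Day 361 only. This stands, and it is why the result is a range starting at 1.0. A reader might infer that an ADA-harm association is built into the tables, or that they would necessarily show more hospitalization among ADA positives. The documents do not support that: persistence removes the effect, and missing Day 361 samples can offset it.

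**It does not reach all tables equally.** This stands. MA LRTI includes outpatients, who give no extra blood. TESAEs include non-respiratory events, which trigger none. In the table of MA LRTI with hospitalization, children admitted with an upper respiratory infection are also sampled more often but count as non-events, which narrows the contrast.

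**The tables are descriptive.** SAP section 4 plans no formal comparison, and the association of ADA with TEAEs and TESAEs is assessed only if data permit. This stands and lowers the severity. The tables are still presented as the evaluation of ADA impact and will be read that way.

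**The SAP may already restrict the samples.** SAP 4.2.5.2 says that ADA data come from the visits scheduled in the protocol. This does not help, because the protocol's schedule (Table 5) includes the blood sample for LRTI admissions.

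**Two SAP 4.1 rules are easily over-read.** A reader might see a cause in the rule that "if both ADA positive and negative samples are available within a subject's visit, ADA positive will be reported". It governs visit-based ADA summaries and adds nothing to an ever-positive status. The rule on LRTI visits chooses between same-day results; it does not define ADA status.

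**The admission sample is informative.** It is the ADA result closest to the event. This stands, and the fix keeps it visible.

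**Conclusion.** The point holds as a detection bias of uncertain and probably small size; severity is minor. The ADA status in the impact tables depends on a sample that one of the tabulated outcomes triggers, and the SAP has no safeguard.

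For one admission at the final analysis, the null odds ratio runs from 1.0, through about 1.05-1.10 under the Phase 1b/2a pattern, to an upper bound of 1.35-1.41. Under the same independence assumption it is about 1.5-1.6 at the Day 151 interims, for children with no Day 361 sample yet, and 1.70-1.88 at the final analysis after two admissions. With one admission each, this is roughly 0 to 2 extra positive children per 100.

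These figures rest on an assumed 10-30% hospitalized and on carrying earlier ADA rates over to immunocompromised children. They compare children admitted for a respiratory infection with those not admitted, so the contrast in the named tables is smaller. The primary safety summaries and the ADA incidence endpoint are unaffected.

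**What to change.** In SAP 4.2.5.2 and 4.2.5.3, state that the post-baseline ADA status used in the ADA-impact tables (TEAE, TESAE, MA LRTI, MA LRTI with hospitalization) is derived from the scheduled Day 31, Day 151 and Day 361 samples only. List or footnote any child who is positive only on an admission-triggered sample. Leave the ADA incidence and prevalence definitions and the by-visit override rule unchanged.

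The cost is one sentence and a filter in the derivation; no procedure changes and no data are lost. The downside is that a transient ADA seen only at admission appears in the listing or footnote and not in the impact-table grouping, so such a child would be positive in the incidence tables and negative in the impact tables. The footnote should say so.

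The fix does not settle the order of ADA and event: a positive first seen at Day 361 would still classify an earlier LRTI. That is a separate point.

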#### 4.2.6 Exploratory analyses

CCI

CCI

#### **4.2.6.4 Healthcare resource utilization (HRU)**

Healthcare resource utilization will be measured as follows:

- Admissions to hospitals and duration of stay.
- Admissions to ICU and duration of stay.
- Requiring respiratory support (using initial/increased CPAP or initial/increased mechanical ventilation) and the duration of use.
- Uses and the duration of use of initial/increased supplemental oxygen.
- Visits to out-patient facilities (urgent care, outpatient ED, outpatient clinic).
- Prescription and OTC medications and duration of use.

These data will be provided through 360 days post dose and will be reported through 150 days post dose, after 150 days post dose, and through 360 days post dose.

Specifically, to report HRU, the following summaries will be repeated for the six endpoints described in [Table 1](#).

- The number and percent of subjects who have had at least one of the following: hospitalization, ICU admission, requiring respiratory support, requiring supplemental oxygen, or visiting an outpatient facility. Similar summaries will be provided by respiratory support subtype (initial/increased CPAP or initial/increased mechanical ventilation) and the type of outpatient facility. The percentage will be calculated for time interval through 150 days post dose, after 150 days post dose, and through 360 days post dose.
- For each of the medical activities listed above, the total number of the activity for a subject who has had at least one respective event in the reporting time-period will be calculated and summarized.
- The total duration of each of the following (in days) will be calculated cumulatively through 360 days post dose and summarized: hospital stay, ICU stay, use of respiratory support, or use of supplemental oxygen for the subjects who has had at least one of the corresponding activities.

The duration of each hospitalization will be calculated from the admission or deterioration date to discharge date. If the discharge date is missing because the subject died in the hospital, the duration of that hospital stay will be calculated from admission to the death date, or end-of-study date, whichever is the earliest. Total duration of hospitalization is the cumulated days of each hospital stay throughout the reporting time-period.

Similarly, the duration of each ICU admission, use of respiratory support, or use of supplemental oxygen will be calculated from start date to stop date, and the total duration of each medical intervention for a subject is calculated by summing the duration of all occurrences in the time interval of interest. If the use of medical intervention occurred multiple times on the same day, the duration of uses in the same day will be counted only once.

In addition, the number of pre-specified OTC medication (analgesics/antipyretics) uses; the number of pre-specified prescription medication (systemic antibacterial agents) uses; and the number of anti-wheezing medication uses will be summarized through 150 days post dose, except for the analgesics/antipyretics uses, which will be summarized through one week after dosing. The Anatomical Therapeutic Chemical Classification System (ATC) codes for these medications will be provided in a separate file by the medical monitor prior to the database lock for the Interim Analysis.

The number and percentage of subjects with pre-specified OTC medications (analgesics/antipyretics) uses within one week after dosing will be provided. The number of uses per subject (for those with the medication use) will be summarized using descriptive statistics. The same summaries will be repeated for subjects with any co-administered routine childhood vaccination (ATC code: J07) within one week of dosing.

The number and percentage of subjects with pre-specified prescription medications (systemic antibacterial agents) uses through 150 days post dose will be provided. The number of uses

per subject (for those with the medication use) will be summarized through 150 days post dose using descriptive statistics.

The number and percentage of subjects with anti-wheezing medications uses through 150 days post dose will be provided. The number of uses per subject (for those with the medication use) will be summarized through 150 days post dose using descriptive statistics.

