2.3 Exploratory Objectives and Associated Endpoints

The exploratory objectives and associated endpoints are described in [Table 3](#).

Table 3 Exploratory Objectives and Associated Endpoints

Type	Objective	Endpoint
CCI		

Table 3 Exploratory Objectives and Associated Endpoints

Type	Objective	Endpoint
CC1		
HRU	To assess HRU for nirsevimab recipients	Magnitude of HRU (eg, number of admissions to hospitals and ICUs and duration of stay; number of subjects who require respiratory support and supplemental oxygen and duration of use; number and type of outpatient visits, eg, ER, urgent care, outpatient clinic; and number of prescription and OTC medications) for nirsevimab recipients

ER = emergency room; HRU = healthcare resource utilization; ICU = intensive care unit; OTC = over-the-counter; RSV = respiratory syncytial virus.

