If signs (such as retractions, rhonchi, wheezing, crackles, or rales) of a new lower respiratory illness occur during a hospitalization, whatever the reason for hospitalization, and there is an objective measure of worsening respiratory status (that is, new requirement for supplemental oxygen, increase in supplemental oxygen requirement from prior to the onset of symptoms, or need for new or additional mechanical ventilation), a specimen will be collected within approximately 2 days from worsening of respiratory status for RSV diagnostic testing by the

central laboratory. For any subject who is hospitalized for a respiratory infection (upper or lower respiratory tract), the subject must return to his/her baseline respiratory status or be clearly resolving the preceding respiratory illness before a subsequent respiratory deterioration for a nosocomial RSV hospitalization event can be determined.

If the RSV diagnostic test (performed centrally via RT-PCR) is positive, the subsequent hospital days will count as a nosocomial RSV hospitalization. The days of RSV hospitalization will be counted beginning with the start of the respiratory deterioration that resulted in the RSV diagnostic test.

RSV LRTI Outpatient Events

Subjects who seek outpatient medical attention, including ER and urgent care visits, for an LRTI should have respiratory secretions obtained within approximately 2 days after the initial healthcare provider assessment.

[figure not shown]
Respiratory Secretions for RSV Detection

Respiratory secretions for RSV testing must be collected from all subjects with LRTIs (inpatient or outpatient) and from all hospitalized subjects with any new respiratory infection (upper or lower) within approximately 2 days after the initial healthcare provider assessment and diagnosis. Nasal secretions will be obtained unless the subject is intubated, and then tracheal secretions may be obtained.

[figure not shown]
Respiratory secretions will be tested in a central laboratory for RSV using the US FDA-cleared and Conformité Européenne or European Conformity-marked in vitro diagnostic real-time RT-PCR assay (Lyra RSV + hMPV assay; Quidel Corporation, San Diego, CA). Testing may include other respiratory pathogens.

The respiratory samples will be retained at AstraZeneca or designee for a maximum of 15 years following the issue of the CSR to properly address potential questions from regulatory authorities.

CC1

CCI

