4.3.4 Healthcare Resource Utilization

Information on HRU will be collected for all events of medically attended LRTI through Day 361 (see Section 4.2). This will include admission to, and duration of hospital and ICU stay, number of subjects who require respiratory support and supplemental oxygen use, duration of respiratory support and supplemental oxygen use, number and type of outpatient visits (eg, ER, urgent care, outpatient clinic), and the number of prescription and over-the-counter (OTC) medications.

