#### **4.1.4.3 Imputation rule for partial concomitant medications dates**

- If a concomitant medication is not associated with an AE:
  - a. Apply general imputation rule described in Section [4.1.4.1](#) wherever it fits.
- If a concomitant medication is associated with an AE:
  - a. The concomitant medication start date will be imputed with either observed or imputed AE start date described in Section [4.1.4.2](#). If there are multiple associated AEs, the earliest AE start date either observed or imputed will be used for imputation.
  - b. The concomitant medication end date will be imputed by the general imputation rule described in Section [4.1.4.1](#) for end date whenever fits. Then compare the imputed concomitant medication start date or end date with the data cut-off and apply the implementation rule for data cut-off for interim analysis described in Section [4.1.5](#). If the imputed concomitant medication end date is after the end of study date, then the concomitant medication end date will be replaced with the end of study date.

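### Two parts of the SAP's HRU analysis depart from the protocol undeclared: medication counts are not tied to LRTI, and the in-hospital death rule counts days before a nosocomial deterioration

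*SAP*

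**What the plan says.** **Protocol.** The objective in 2.3 is general: "To assess HRU for nirsevimab recipients". The collection rule in 4.3.4 is specific: "Information on HRU will be collected for all events of medically attended LRTI through Day 361". Its list of items ends with "and the number of prescription and over-the-counter (OTC) medications". Table 5 agrees: HRU is marked only in the LRTI column, for Days 1 to 361, and footnote g includes medications. For nosocomial RSV, 4.3.1.1 fixes where the count of days starts: "The days of RSV hospitalization will be counted beginning with the start of the respiratory deterioration".

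**SAP, non-medication items.** Section 4.2.6.4 states: "Specifically, to report HRU, the following summaries will be repeated for the six endpoints described in" Table 1. The summaries that follow cover hospital and ICU admission, respiratory support, supplemental oxygen and outpatient visits.

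**SAP, medications.** The opening list of 4.2.6.4 includes prescription and OTC medications with their duration of use, and promises reporting for three periods: up to 150 days, beyond 150 days, and up to 360 days after dosing. The detailed paragraphs later in the section give something else: "the number of pre-specified prescription medication (systemic antibacterial agents) uses; and the number of anti-wheezing medication uses will be summarized through 150 days". Analgesics/antipyretics are counted for one week after dosing, and that count is repeated for children with a co-administered routine vaccine. Records are to be selected by ATC code.

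**SAP, length of stay.** The general rule starts the count at the admission date or the deterioration date. The next sentence deals with a discharge date that is missing because the child died in hospital: "the duration of that hospital stay will be calculated from admission to the death date", or to the end-of-study date if that is earlier.

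**SAP Section 6** lists the unplanned interim analysis and the new PK summary rules. It says nothing on HRU.

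**The concern.** The protocol collects medication use as part of the care given for an LRTI. A count of every systemic antibacterial or anti-wheezing record in the first 150 days measures something else, and a first-week antipyretic count is closer to a tolerability measure. The enrolled children have transplants, chemotherapy, HIV, primary immunodeficiency or other immunosuppression (protocol 4.1.2), and every concomitant medication from screening onward is recorded (protocol 4.7). Background antibacterial use is therefore plausible, although the documents give no rate. With no comparator arm, nothing in the design separates it from care for RSV illness.

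The death rule is a separate matter. Followed literally, it attributes to RSV the inpatient days that came before the RSV illness. Few RSV stays are likely among about 100 children, so one such stay could visibly shift a mean duration.

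**Working it through.** The documents give no HRU figure to reproduce, so the check is mainly a comparison of texts. The arithmetic only sets a scale.

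**1. Medication component, protocol against SAP**

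| Feature | Protocol 4.3.4, Table 5 | SAP 4.2.6.4, opening list | SAP 4.2.6.4, detailed paragraphs |
|---|---|---|---|
| Unit | Medically attended LRTI event | Not stated | Subject and drug class, no LRTI filter |
| Antibacterial, anti-wheezing | To Day 361 | Three periods to 360 days | To 150 days |
| Analgesic/antipyretic | To Day 361 | Three periods to 360 days | First week after dosing |
| Duration of use | Not in 4.3.4; Table 5 footnote g still mentions days | Listed | Not delivered |

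Share of the 360-day post-dose follow-up covered:
- antibacterial and anti-wheezing: 150/360 = 41.7%, so 360 − 150 = 210 days have no specified medication summary;
- analgesic/antipyretic: 7/360 = 1.9%.

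For antibacterial and anti-wheezing drugs within the first 150 days, the unfiltered count cannot be smaller than the LRTI-linked count. How much larger it is depends on background use, which the documents do not give. For analgesics no direction can be stated: the first-week count may include use unrelated to LRTI, and it misses LRTI use after Day 7.

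**2. Do the medication counts enter the other HRU results?** No. They are introduced as additional summaries, and the composite of subjects with at least one HRU item contains no medication item.

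**3. Death rule.** Let L be the inpatient days before the respiratory deterioration and k the days from deterioration to death.
- Protocol 4.3.1.1, and the SAP's general rule when started at deterioration: k days.
- SAP in-hospital death rule: L + k days. The excess is L.

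Illustration: k is set to 11.5 or 24 days, the range protocol 1.1 quotes for prolonged RSV hospitalization, borrowed only as a scale. L is assumed.

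| L (assumed) | k | Protocol count | SAP death rule | Ratio |
|---|---|---|---|---|
| 7 | 11.5 | 11.5 | 18.5 | 1.61 |
| 7 | 24 | 24 | 31 | 1.29 |
| 30 | 11.5 | 11.5 | 41.5 | 3.61 |
| 30 | 24 | 24 | 54 | 2.25 |

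Effect on a mean over m hospitalized children (m assumed), each with 11.5 days, one of them a fatal nosocomial case: mean = 11.5 + L/m.
- m = 2: 15.0 (L = 7) or 26.5 (L = 30)
- m = 5: 12.9 or 17.5
- m = 10: 12.2 or 14.5

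**4. Declaration.** SAP Section 1 commits to describing any change from protocol specifications in Section 6. Neither departure is there.

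**The case against.** The case for leaving the plan alone has several parts.

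- **Most HRU is event-based.** A reader might infer that the LRTI-based HRU of the protocol is not reported at all. The SAP does not support that: every non-medication item is repeated for the Table 1 endpoints. Four of the six endpoints are redacted, so whether they cover all medically attended LRTI cannot be checked, and the redaction is not a fault. This part of the objection stands and confines the point to medications and one duration rule.
- **The protocol objective is broad.** Sections 2.3 and 4.8.7.4 do not mention LRTI; the restriction comes from 4.3.4 and Table 5. Counting drug classes per subject is therefore a permissible addition. It does not replace the LRTI-linked count that the collection rule implies, and it leaves the SAP's own conflict over periods and duration unresolved.
- **The change is visible.** SAP 3.3.4 names the drug-class measures and the amendment history records the move to them. It is not concealed, but Section 6 is where the SAP says such changes will appear.
- **The LRTI-linked table may exist elsewhere.** The opening list could be tabulated under specifications held in a separate document. That is possible, so it goes too far to say that LRTI medication use will never be produced. The SAP text does not specify it.
- **The death rule is narrow and may be shorthand.** It needs a nosocomial event, an in-hospital death and a missing discharge date, and the sentence before it already names the deterioration date. Protocol 4.3.1.1 also classes demonstrated RSV deaths as primary RSV hospitalization endpoints, which blurs the category. The rarity stands. But a programmer following the sentence would start at admission, and the classification of the endpoint does not change where the nosocomial day count starts.
- **Size.** A reader might infer that a reported HRU percentage would be heavily inflated by background antibacterials. No such percentage can be derived: the rates are not in the documents, and the drug classes are reported separately. Medians and ranges are reported along with means.

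**Conclusion.** The point holds in limited form. The medication part of HRU is not LRTI-based as specified, its windows contradict the opening list of the same section, and the in-hospital death rule conflicts with protocol 4.3.1.1 and with the SAP's preceding sentence. Neither departure is declared in Section 6.

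The coverage shares (41.7% and 1.9% of the post-dose period) and the excess of L days follow from the text. The values of L, k and m above are illustrative, and the background rate of antibacterial use is unknown, so no effect on the trial's actual HRU results can be stated. HRU is exploratory, the study is descriptive with no formal comparisons, and no safety, PK, ADA or efficacy result is affected. Correction is still worthwhile because these are stated rules that would give the wrong quantity if followed, and they can be amended cheaply.

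**What to change.** 1. **Death rule.** Start the stay from admission or, for nosocomial events, the deterioration date, and keep the existing end-point. This is a one-phrase change.
2. **LRTI-linked medication summaries.** Count prescription (systemic antibacterial, anti-wheezing) and OTC (analgesic/antipyretic) records linked to a medically attended LRTI and starting on or after its onset. Report them for the three periods already promised.
3. **Existing counts.** Keep the drug-class counts to 150 days and the first-week analgesic count, but label them general concomitant medication use rather than HRU.
4. **Duration of medication use.** Either specify it or remove it from the opening list, and reconcile this with protocol 4.3.4 and Table 5 footnote g.
5. **Section 6.** Record any departure from protocol 4.3.4 that remains.

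**Cost.** SAP wording, one date change in the duration derivation, and a filter on existing data. The link appears to be available: SAP 4.1.4.3 has a rule headed "If a concomitant medication is associated with an AE", and SAP 4.2.5.3 already plans a mapping of AE terms to LRTI before database lock. No new data collection appears necessary. The drawback is that LRTI-linked counts will be small and any use not linked to an AE will be left out, which is a reason to keep the general counts beside them.
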